## 6.4.2.3 Home Blood Pressure Monitoring

Pending funding, home blood pressure measurements will be collected using QardioArm, which is a wireless blood pressure device validated for measuring blood pressure and heart rate in participants with an arm circumference of 22-35 cm. At selected sites, a pilot study will be conducted in which home BP measurements will be collected to assess the feasibility of obtaining home BP measurements among CKiD participants who have not initiated RRT. Home BP monitoring will be performed beginning at visit 2 and then every year thereafter. Participants will be given the QardioArm device to take home to collect data over the course of 3 days.

# 6.4.2.4 Cardiac Magnetic Resonance Imaging (MRI)

To assess heart disease and conditions, cardiac MRIs will be performed on a sub-set of the cohort who are eight (8) years old or older at regular, irregular and post-RRT study visits. The cardiac MRI will be performed as long as the participant is able to tolerate the procedure without sedation. Deep sedation, general anesthesia or anxiolytics is not permitted. For participants who have not initiated RRT, it will be measured on children with a high probability of reaching ESRD. For these participants, the cardiac MRI will be performed at the next study visit after a participant reaches an estimated GFR less than or equal to 30 ml/min|1.73m^2, or at an irregular visit prior to the initiation of RRT, whichever occurs first. However, after the initiation of RRT, the cardiac MRI will be performed at post-RRT visits among participants who meet the age requirement regardless of their estimated GFR measurements. Refer to Section 5.4.4 for details regarding post-RRT (i.e., post-transplant and post-dialysis) visits.

# 6.4.3 Outcome Measures

review An Outcomes Adjudication Committee will potential cardiovascular hospitalizations using discharge summary and laboratory reports from these hospitalizations. If the clinical center determines that a cardiovascular event may have occurred during a hospitalization, a discharge summary will be obtained from that hospitalization and forwarded for distribution to the Outcome Adjudication Committee. The committee will then determine outcome status based on the discharge summaries. A cardiovascular outcome will include: sudden cardiac death OR hospitalizations for cardiomyopathy, congestive heart failure, and/or arrhythmias. Patient hospitalizations will also be reviewed for the occurrence of an increase in the dose of diuretics, ACE inhibitors or Angiotensin Receptor Blockers. Because children with CKD are unlikely to develop symptomatic cardiovascular disease, intermediate cardiovascular outcomes found during echocardiographic evaluation also will be evaluated. Specifically, new onset of LVH and LV dysfunction will be reported.

The primary outcomes will be the levels and within-individual changes of cardiovascular markers (e.g., Clinical BP, summary measures of echocardiography). Of particular interest will be the analysis of the association between decline in GFR and risk of progression of CVD as determined by changes in markers of CVD.

# 6.5 Growth Measures

CKD has a negative effect on linear growth, ultimately leading to decreased adult height in many patients. Along with affecting adult height, poor growth in children with CKD is associated with increased morbidity and mortality [Furth 2000, Furth 2002a, Furth 2002b, Wong 2000]. Finally, there is currently limited data on the influence of poor linear growth on neurocognitive and cardiovascular outcomes.

## 6.5.1 Core Tests

The core tests to measure growth are:

- Height/Length
- Body Mass Index
- Circumferences (Head, arm, waist and hip)
- Parathyroid Hormone (intact)
- High Sensitivity C-Reactive Protein
- Vitamin D
- Fibroblast Growth Factor 23 (FGF-23)
- Food Frequency Questionnaire
- Grip Strength

## 6.5.1.1 Height/Length and Body Mass Index (BMI)

Height/length and body mass index will be measured at every study visit for the entire cohort. Children will be measured in bare feet. Height will be measured using a stadiometer in all children > 2 years who can stand. Length will be measured in children less than age 2 or who are unable to stand by using a firm box in the supine position. If possible, parental height will also be measured at the first baseline visit (V1a). The techniques and equipment for measuring height/length will be reviewed with the principal investigator and study coordinator at each study site.

Height Standard Deviation Score (SDS) ([observed height – mean height for age]/height SDS for age) will be calculated based on chronologic age and gender using normative data for the US population. Linear growth will be evaluated as height SDS and change in height SDS over time. Change in height SDS will be expressed as annualized data. In addition, height velocity SDS will be calculated.

BMI will be calculated as weight (kg)/[height (m)]. Percentiles of BMI will be calculated using standard US charts.

### 6.5.1.2 Circumferences

Circumferences to be measured will include head and mid arm to the nearest 0.1 cm and, waist and hip circumference to the nearest 0.3 cm. At every visit, head circumference will be measured for children 3 years old and younger. Mid arm circumferences will be measured for the entire cohort. Waist and hip circumferences will also be measured for the entire cohort except for children 12 months old and/or younger who are unable to stand. The measure will use a tape with units of cm and not pinch or compress the tissue while taking measurements. More detailed descriptions of the procedures for circumference measurements and calculations will be included in the Manual of Procedures.

## 6.5.1.3 Intact Parathyroid Hormone (iPTH)

The ADVIA Centaur Intact PTH assay is a two-site sandwich immunoassay using direct chemiluminometric technology.

## 6.5.1.4 High Sensitivity C-Reactive Protein (hsCRP)

Given the increasing evidence for the importance of inflammation as a marker for mortality and declining albumin in patients with CKD [DeFilippi 2003, Eustace 2004, Kaysen 2004], inflammation may be an important variable affecting growth in children with CKD. High sensitivity CRP will be measured centrally at baseline and then every other year thereafter.

### 6.5.1.5 Vitamin D

Patients with CKD are at higher risk of vitamin D deficiency. They are also more likely to have lower levels of vitamin D in comparison to those with no kidney disease for a variety of reasons. We will explore the association between vitamin D deficiency and the risks associated with each of the scientific domains (CKD progression, growth, cardiovascular and neurocognitive and behavioral.) 25 Hydroxy Vitamin D will be measured centrally at baseline and then every other year thereafter.

## 6.5.1.6 Fibroblast Growth Factor 23 (FGF-23)

FGF-23 is a bone-derived circulating hormone and an important regulator of phosphate and vitamin D homeostasis. In adult CKD patients, increased FGF-23 concentration is a key factor associated with morbidity and mortality; however, the mechanism by which FGF-23 concentrations are increased in chronic kidney disease is unknown. We will explore the association between increased FGF-23 concentrations and growth retardation, CKD progression and risk factors for cardiovascular disease. FGF-23 will be measured centrally at baseline and then every other year thereafter.

### 6.5.1.7 Food Frequency Questionnaire (FFQ)

The Food Frequency Questionnaire was completed on a yearly basis beginning at the second baseline visit (V1b). During the study visit, the parents and/or child were instructed to complete the age appropriate FFQ and returned the completed form to the clinical site study coordinator. When the family returns the FFQ to the study coordinator, the study coordinator reviewed the forms for completeness. If there were missing information, the study coordinator clarified with the family and sent the completed FFQs to the Clinical Coordinating Center with the other study forms. As of the June 2014 amendment, the study discontinued collecting FFQ data.

### 6.5.1.8 6 Minute Walk Test (6MWT)

The 6 minute walk test was completed at visit 3 and then every year thereafter to measure functional capacity. The primary measurement of interest was the total distance walked. The study coordinators instructed the participant to walk as far as they can for six minutes. The 6MWT was done indoors in an appropriate corridor using cones to mark distance, or outdoors on a flat surface. The study coordinator recorded the distance walked, measured and recorded the participant's leg length and sent the data to the Clinical Coordinating Center. As of the June 2016 amendment, the study discontinued completing 6MWT.

## 6.5.1.9 Grip Strength Test

The grip strength test is used to measure maximal voluntary grip strength. For participants who are six (6) years old or older, a grip dynamometer will be used to measure grip strength at visit 3 and every other year thereafter.

### 6.5.2 Non-Core Tests

## 6.5.2.1 Physical Activity Monitoring

Pending funding, physical activity will be measured using an Actigraph Link device. The Actigraph Link device is an FDA-approved accelerometer frequently used for research purposes to assess physical activity. The device will be utilized to assess physical activity in a subset of participants at selected clinical sites. The device will collect 8 days of continuous wear data and monitoring will be performed at visit 1b and every year thereafter.

### 6.5.3 Outcome Measures

The core studies of this proposal will look at 2 principal questions. First, what variables affect growth? Second, does poor growth predict a poor outcome? The variables in the core study that may influence growth are listed in the following table:

Variable	Method of Measurement
Pubertal status and BMI	Physical examination
Serum albumin (and urine protein), GFR	Laboratory measurement
Calcium, phosphorus, bicarbonate, CRP, PTH, vitamin D	Laboratory measurement
Gender and Race	History
Type and Length of kidney disease	History
Co-morbidities, surgeries, medications	History
Birth weight and height and gestational age	History
Parental heights	History and direct measurement
Grip Strength	Study form filled out by coordinator

Variables Affecting Growth

Analysis will look at growth as the dependent variable using both current height SDS and growth velocity SDS.

The relationship between linear growth and the following outcomes will be analyzed: Neurocognitive Tests (Activity Level tests, Cognitive and Developmental Tests, Behavior Assessment Tests), Cardiovascular Outcomes (Hypertension, Left ventricular hypertrophy) and Morbidity and Mortality (Hospitalization Rate, Mortality). Analysis will focus on the relationship between current height (height SDS) and current growth velocity (height velocity SDS) and the various outcomes. In addition, the effect of covariates (e.g., inflammation, comorbidities) will be analyzed.

The data to be collected by CKiD will allow us to categorize the extent to which a decline in GFR is related to growth failure. The study has been designed to have the assessment of the changes in GFR precede the assessment of growth.

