- 11. Growth failure will be associated with the severity of secondary hyperparathyroidism, biomarkers of inflammation, poor nutrition, extent of GFR decline and early age at onset (i.e., prolonged duration of CKD).
- 12. Growth failure in children with CKD will be associated with a higher rate of morbidity, including increased hospitalizations, decreased quality of life, poor neurocognitive outcome and increased cardiovascular complications.
- 13. The response to recombinant human growth hormone (rhGH) treatment will be positively associated with GFR, serum bicarbonate level and nutritional status and negatively correlated with high sensitivity C reactive protein level, and severity of secondary hyperparathyroidism.

The proposed cohort study has been designed to measure variables in four scientific domains: kidney, neurocognition, cardiovascular and growth. The protocol was determined to optimize the power of the cohort design whereby levels and changes of exposure of interest temporally precede outcomes.

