#### 6.1.3 Medical History Information

6.1.3.1 Kidney Disease History: Detailed information on the subjects' underlying kidney disease and other disease comorbidity will be obtained from parent/guardian interview and by chart review in a standardized fashion at the time of the eligibility or baseline visit.

A medical chart review will obtain documentation of the underlying diagnosis of kidney disease from clinical history, pathologic (biopsy) diagnosis, kidney/bladder ultrasound and other renal imaging studies. The chart review will also obtain documentation of diagnosis of other diseases (i.e., lung, genitourinary and infectious disease). We will also collect information on history of surgical interventions and urologic surgeries, including their type and timing.

Information on age at diagnosis of kidney or urologic disease, age at onset and estimated GFR at diagnosis will be collected from structured parent/guardian interview and chart review.

6.1.3.2 Health Care Utilization: Health care resource utilization data will be collected using questionnaires and data obtained directly from CKiD subjects via annual inperson interviews.

6.1.4 Physical Symptoms: Information on kidney disease-related symptoms will be collected from structured subject and parent interviews. Children between the ages of 8 and 16, and parents/guardians of children under the age of 8, will be interviewed to obtain symptoms data. Questions about the quality and quantity of sleep will also be included in the symptoms questionnaire.

6.1.5 Assessment of Dietary Intake: Information on any herbal remedies, health supplements and/or vitamins will also be collected from structured interview at annual visits.

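### Section 6.5.3 asks whether poor growth predicts poor outcome but uses current height and current growth velocity as exposures, without requiring growth to precede the outcome interval

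*Protocol*

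**What the plan says.** Section 6.5.3 sets two core growth questions. The first is what affects growth. The second is directional: "Second, does poor growth predict a poor outcome". The outcomes listed for it are neurocognitive tests, hypertension, LVH, hospitalisation rate and mortality. The exposures are stated: "Analysis will focus on the relationship between current height (height SDS) and current growth velocity (height velocity SDS) and the various outcomes". On adjustment it says: "In addition, the effect of covariates (e.g., inflammation, comorbidities) will be analyzed". The timing of those covariates is not given. The only order the section fixes concerns a different pair of variables: "The study has been designed to have the assessment of the changes in GFR precede the assessment of growth".

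Other sections bear on this:

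- Section 1.3 says the protocol was chosen to "optimize the power of the cohort design whereby levels and changes of exposure of interest temporally precede outcomes".
- Section 1.2 words Aim 4 in terms of the consequences of growth failure for morbidity. Hypothesis 12 in section 1.3 claims only an association.
- Section 2.4 leaves open whether growth failure causes worse outcomes or only marks sicker children.
- Section 6.1.3.2 says: "Health care resource utilization data will be collected using questionnaires and data obtained directly from CKiD subjects via annual inperson interviews".
- Section 5.4.1 has annual visits look back to the previous contact for clinical events related to the primary outcomes. It also places the growth and neurocognitive components at the same time.

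**The concern.** A question about prediction needs the predictor to come first. Height velocity at a visit is computed from the preceding heights, so it summarises a period that has already passed. If the outcome is what was reported or measured at the same visit, exposure and outcome share that period, or the outcome came earlier within it. A year of illness can both put a child in hospital and slow growth, and the analysis would show slow growth going with hospitalisation even if growth had no effect.

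The two questions in section 6.5.3 would also become hard to separate. Comorbidities are listed there among the variables that affect growth, while hospitalisation, hypertension and LVH are listed as outcomes of growth, and current height and velocity scores serve both analyses. One same-period association could be cited in either direction. At stake are the cause-or-marker question of section 2.4 and the part of Aim 4 that concerns consequences.

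**Working it through.** **1. Timing.** The protocol gives no sample size, power or effect estimate for growth as a predictor, so there is no figure to reproduce. Let visit j fall at time t(j). Velocity at j is (height at j − height at j−1) / (t(j) − t(j−1)), which describes the interval from j−1 to j.

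| Outcome | Period it reflects if taken at visit j | Order relative to current velocity |
|---|---|---|
| Hospitalisation reported at j | Past interval (annual interview, 6.1.3.2; recall period not stated there) | Overlaps |
| Neurocognitive score at j | Same visit as growth (5.4.1) | Concurrent |
| Hypertension classified at j | Same visit (blood pressure at every visit, 6.4.1.1) | Concurrent |
| LVH against height level | Echocardiogram from visit 2 (6.4.1.3); heights already taken at V1a and V1b (Table 5.4.1a) | Height can precede; problem not shown |
| Mortality | After the height measurement | Growth precedes |

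**2. Comparison with GFR as exposure.** Sections 8.2.1 and 8.2.3 use GFR decline over the year before the outcome visit. Section 8.2.2 uses the year before the baseline heart measurement. The protocol therefore fixes order when GFR is the exposure. Its only worked growth model (8.2.3) has growth as the dependent variable.

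**3. Illustration A (all inputs assumed).** 900 children, 5 years, 15% hospitalised per year, no effect of growth; a hospital year lowers that year's velocity by d = 0.2, 0.3 or 0.5 SD. With unit SD within groups, the odds ratio per SD lower velocity is exp(d): exp(0.2) = 1.22, exp(0.3) = 1.35, exp(0.5) = 1.65. Simulation (300 replicates) gave 1.22, 1.35 and 1.66, significant in every run. Velocity from the preceding interval gave 1.00 with 5% rejection. Illness has no carry-over between years in this set-up.

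**4. Illustration B (all inputs assumed), with persistent illness.** Latent illness S is standard normal with year-to-year correlation ρ. Hospitalisations are Poisson with rate 0.3·exp(0.7·S). Velocity is −b·S plus noise, with total SD 1, and growth has no effect. The expected rate ratio per SD lower velocity is exp(0.7·b) in the same year and exp(0.7·ρ·b) in the next.

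- Same year, b = 0.1, 0.3, 0.5: exp(0.07) = 1.07, exp(0.21) = 1.23, exp(0.35) = 1.42. Simulated values ran from 1.06 to 1.43.
- Next year, ρ = 0: 1.00 for every b.
- Next year, ρ = 0.5: exp(0.035) = 1.04, exp(0.105) = 1.11, exp(0.175) = 1.19. Simulated: 1.04, 1.11, 1.19.
- Next year, ρ = 0.8: exp(0.056) = 1.06, exp(0.168) = 1.18, exp(0.28) = 1.32. Simulated: 1.06, 1.18, 1.33.
- Next year, also adjusted for hospitalisation in the velocity year (simulated, b = 0.1, 0.3, 0.5): 1.00 throughout at ρ = 0; 1.03, 1.09, 1.17 at ρ = 0.5; 1.05, 1.15, 1.27 at ρ = 0.8.

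The overall span of 1.06 to 1.66 mixes rate ratios (B) with odds ratios (A). Both illustrations cover velocity against hospitalisation only.

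**The case against.** A reader might infer that section 6.5.3 plans to test outcomes from the same or an earlier period and to report the result as growth failure causing illness. The documents do not support that. The section gives no outcome window, and the overlap is inferred from the word *current* and the visit schedule. Section 6.1.3.2 states no recall period, and the look-back in section 5.4.1 concerns events related to the primary outcomes. Hypothesis 12 claims association only, and section 6.5.3 speaks of a relationship and of prediction; only Aim 4 is worded causally.

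It can also be said that a lag belongs in an analysis plan, and that the study-wide ordering principle of section 1.3 fills the gap. Section 2.1 names reverse causality, and section 8.1.1 names marginal structural models for feedback over time. Finally, the simulated sizes are assumed, and a lagged ratio of 1.00 holds only for transient illness.

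The points about wording, mortality, LVH and size stand and limit the finding. The analysis-plan argument does not dispose of it: section 6.5.3 does more than omit a lag, because it names an exposure that fits the question poorly. The general principle in section 1.3 is not carried into that choice. The methods in section 8.1.1 are to be explored, are framed around treatment, and are not assigned to growth as exposure.

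**Conclusion.** The point holds in limited form. The stated exposures do not secure growth before outcome, which sits badly with section 1.3, with Aim 4 and with the question itself. It bears on velocity against hospitalisation reported at the same visit, against same-visit neurocognitive scores, and against hypertension if classified at that visit. It does not bear on mortality, and it is not shown for height level against LVH.

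The direction of the possible bias is clear: towards Hypothesis 12 when illness slows growth. Its size is not known from the documents. Under the assumptions above, a null effect appears as a ratio of about 1.06 to 1.66 per SD lower velocity. A one-year lag removes it if illness is transient. With strongly persistent illness (ρ = 0.8, b = 0.5), up to 1.33 remains after the lag and 1.27 after also adjusting for hospitalisation in the velocity year.

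**What to change.** Replace the sentence on current height and velocity in section 6.5.3 with an ordered analysis:

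- **Exposure:** height SDS and height velocity SDS using measurements up to visit j−1.
- **Outcome:** hospitalisation, new-onset hypertension or LVH, and change in test scores after j−1. For neurocognitive tests and echocardiograms, take j−1 as the previous occasion on which that outcome was assessed, since these are not annual.
- **Adjustment:** GFR, hospitalisation or other morbidity, and outcome status measured before the growth interval. Alternatively, assign the marginal structural approach of section 8.1.1 to this question.
- **Same-visit associations:** keep them, labelled descriptive.
- **Limitation to state:** a lag reduces but does not remove the bias when illness persists. The adjusted residuals above come from adjusting for hospitalisation within the velocity year; adjustment confined to earlier morbidity was not simulated. A sensitivity analysis adding hospitalisation during the growth interval would show how much depends on this, though it may also adjust away part of any real growth effect.

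No new data are needed, because section 6.5.1.1 has height measured at every visit. The cost is a change of analysis wording and the loss of the first growth interval as run-in.

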# 7. ANCILLARY STUDIES

To enhance the value of the CKiD study, the steering committee welcomes proposals from investigators to carry out ancillary studies. (See Section 3.8) Investigators are encouraged to submit proposals that deal with CKiD specific aims and associated hypothesis. Ancillary studies enable investigators to address questions of scientific relevance. Due to financial constraints, these studies were unable to be included as either core or non-core measures. CKiD has identified studies of interest that are related to the four specific aims and pending funding these proposed ancillary studies will be conducted.

